Smoking Status: At least 100 cigarettes in entire life	National Health Interview Survey 
Smoking Status: Years as a smoker	Lung Cancer Screening Decision Tool 
Smoking Status: Current smoking	Current MSK Survivorship Patient Assessment (Based on the National Health Interview Survey)
Cigarettes per day	Current MSK Survivorship Patient Assessment
Alcohol use	The CAGE questionnaire 

**4.2.2 The Treatment Checklist** (Appendix B) collects claims data about the head and neck cancer diagnosis and treatment, which will then be translated into lay language. This will be done differently at the two participating sites. At MSK, HN-STAR generates an Automated Treatment Checklist, which presents an organized list of diagnosis, staging and treatment received at MSK using claims data from billing codes in the MSK record. The NP is prompted to verify the accuracy of the presented list and make necessary corrections. At HH, where claims data will not be automatically ported to HN-STAR, there is a Manual Treatment Checklist, in which all possible diagnosis and treatment options are presented as an organized checklist. The NP must manually complete the Manual Treatment Checklist by referring to the patients' medical records. At either institution, once a patient has agreed to participate in the study, prior to the participant's survivorship clinic visit, the NP will verify or complete the checklist. The checklist will result in the generation of a lay language treatment summary that will appear in the Survivorship Care Plan (described below in section 4.2.4). The NPs at both sites will be trained on how to use the Treatment Checklist.

**4.2.3 The Interactive Discussion Guide** (Appendix M) integrates data from the Survivor Self-Assessment, data from the Treatment Checklist, and data regarding evidence-based survivorship care. Three algorithms will then use these data to generate the Interactive Discussion Guide that the NP can use during the routine visit.

1. *Treatment algorithms* use Current Procedural Terminology (CPT) codes and National Comprehensive Cancer Network (NCCN) guidelines to generate personalized surveillance recommendations (e.g., annual thyroid studies for survivors who received radiation to neck).

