#### **4.2.5 Clinical flow using HN-STAR**

1. *Before the survivorship visit:* At MSK, the institutional database of CPT codes will automatically populate the Automated Treatment Checklist in HN-STAR, and the NP will verify its accuracy. At HH, the NP will complete the Manual Treatment Checklist. At both sites, the Treatment Checklist will inform treatment-based recommendations in the Interactive Discussion Guide and generate a plain-language treatment summary for the Survivorship Care Plan.
2. *Before the survivorship visit,* survivors will complete the online Survivor Self-Assessment. Using the Survivor Self-Assessment and Treatment Checklist data, HN-STAR will create the Interactive Discussion Guide for the clinic visit that presents 1) an oncologic surveillance schedule, 2) a list of severity-based symptom management options, and 3) personalized preventive care and screening recommendations.
3. *During the visit,* the NP will use the Interactive Discussion Guide to facilitate conversation. Specifically, the NP and survivor will discuss ongoing care, select plans for symptom management, and identify who is responsible for each action (NP, survivor, or primary care provider).
4. *At the end of the visit,* the Treatment Checklist will be combined with the selected plan of care from the visit in the Survivorship Care Plan. At the end of the visit, the Survivorship Care Plan will be given to the survivor and discussed with the survivor. For Aim 1: Part 2, after the visit, the Survivorship Care Plan will be sent to each survivor's primary care provider.

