### **7.3 Passively Collected Data**

In addition to surveys, patient and nurse practitioner data will be recorded through the web interfaces of HN-STAR. In addition, NPs will document clinic notes as part of routine care. These data will be used to inform feasibility of HN-STAR and contribute to power calculations for the future multi-site randomized controlled trial.

**7.3.1** For all visits at MSK, preceding the patient visit, the NP will verify the Automated Treatment Checklist. When the NP makes any changes to imported data and verifies the final Treatment Checklist, these data will be collected. These data will inform the accuracy of the automatically generated treatment summary and the time required to verify the information.

**7.3.2** For all visits at HH, preceding the patient visit, the NP will complete the Manual Treatment Checklist. Data will be collected regarding the time required to complete the checklist.

**7.3.3** All patients will complete the Survivor Self-Assessment before their clinic visit. HN-STAR will record the amount of time taken, the items skipped, and the proportion of the Self-Assessment completed.

**7.3.4** As part of routine care, the NP will record topics addressed and actions taken in the clinic note for each visit. Clinic notes regarding the identification and management of late effects will be abstracted.

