## 11.0 BIOSTATISTICS

**11.1 Sample size.** This feasibility study is not powered to test formal hypotheses. Instead, it will provide feedback regarding the HN-STAR process. We will enroll 10 patients in Aim 1: Part 1. In Aim 1: Part 2, we will enroll 45 additional patients: 30 from MSK and 15 from HH. The MSK clinic sees over 20 patients per month, ensuring that enrollment is attainable. The HH clinic sees approximately 8 patients per month. We anticipate that enrolling 45 patients will not take longer than 6 months. Enrolling PCPs may be more difficult; we anticipate that not all 45 PCPs will complete the Primary Care Provider Survey. Part of our feasibility study is to test whether this method of recruitment and level of incentives will be adequate to recruit PCPs in a future study, and the level of participation will inform this feasibility outcome. Both NPs are integrally involved in implementing HN-STAR in their clinics.

### 11.2 Analysis Aim 1: Parts 1 and 2

The structured survey questions (asked of survivors, NPs, and PCPs in Aim 1: Parts 1 and 2) will be summarized using descriptive statistics. Quantitative outcomes will include survivors' rates of completion of the self-assessment, survey completion rates for survivor, NP, and Primary Care Provider Surveys in the feasibility study. The number of questions to answer is different between surveys and even between respondents, based on skip patterns built into the electronic survey platform. Each survey will be considered complete if at least 75% of questions that are asked are answered. WebCore will automatically capture the percentage of questions that are answered for each survey administered. We will also look at survivor responses by race and ethnicity. Other quantitative outcomes include the median time survivors required to complete the self-assessment, the accuracy of the automated treatment summary (verified against the EMR), the time required for NP verification of the treatment summary, and the length of HN-STAR visits.

Each component of HN-STAR will be evaluated individually for feasibility. We will consider the Survivor Self-Assessment feasible for subsequent effectiveness testing if the following criteria are met:

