- >75% survivors completed >75% of self-assessment. The survivor self-assessment has multiple components that include a total of 47 items for men and 49 items for women. We will only include items that are asked of every participant (i.e. no sub questions) for this metric. We will consider 75% of the self-assessment complete if 36 items (for men) and 37 items (for women) are completed.
- The mean proportion of assessment completed >75%.
- The median time to complete self-assessment <15 minutes.
- >50% of survivors rate the Self-Assessment visit positively on the Survivor Post Assessment Survey (Appendix D). For items #13, a response of "No" is positive, for item #14, a response of "yes" is positive, for item #15, a response of "Just right" is positive, and for items 16-18, a response of "Agree" or "Strongly agree" is positive. We will consider a positive overall rating if >50% of responses are positive.

We will consider the Automated Treatment Checklist feasible if the following criteria are met:

- >90% of the treatment summaries were deemed accurate .
- The median time to verify the summary <20 minutes.

We will consider the Manual Treatment Checklist feasible if the following criteria are met:

- The median time to complete <30 minutes. (In practice, survivorship care plans typically take an hour or more to complete.)

The Interactive Discussion Guide will be considered feasible if the following criteria are met:

- >75% of discussion guides did not miss relevant information. We will determine whether relevant information was covered using item #6 from the Nurse Practitioner Survey (Appendix F) for this metric. Responses of "Agree" or "Strongly agree" to the item, "the discussion guide missed important information about the patient will be measured as missing relevant information.
- >50% of survivors rate the survivorship visit positively on the Survivor Post Assessment Survey (Appendix E). For items #1-8, a response of "Agree" or "Strongly agree" is positive. We will consider a positive overall rating if >50% of responses are positive.
- The median visit time <50 minutes (current visit time average is 40 minutes).

The Survivorship Care Plan will be deemed feasible if the following criteria are met:

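### The Manual Treatment Checklist at HH is judged feasible on completion time alone, so transcription errors cannot affect the verdict

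*Combined protocol and SAP*

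**What the plan says.** The Treatment Checklist exists in two versions (4.2.2). At MSK it is filled from billing codes, and the nurse practitioner (NP) verifies and corrects it. At HH nothing is imported: "The NP must manually complete the Manual Treatment Checklist by referring to the patients' medical records".

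Section 11.2 evaluates each component individually. The automated version has two criteria: ">90% of the treatment summaries were deemed accurate" and "The median time to verify the summary <20 minutes". The manual version has one: "The median time to complete <30 minutes".

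Data collection follows the same pattern. For MSK, 7.3.1 records the changes that the NP makes to the imported list and adds: "These data will inform the accuracy of the automatically generated treatment summary and the time required to verify the information". For HH, 7.3.2 says only: "Data will be collected regarding the time required to complete the checklist".

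The two versions have the same use. Section 4.2.5 states: "At both sites, the Treatment Checklist will inform treatment-based recommendations in the Interactive Discussion Guide". It also has both versions generate the plain-language treatment summary in the Survivorship Care Plan. If a component misses any of its criteria, 11.2 says that adaptation and further testing will be considered.

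**The concern.** A form completed by hand can be quick and still omit a treatment or record the wrong one. The manual version has no criterion that would show this. Its errors would pass into the surveillance recommendations that the NP sees and into the summary sent to the survivor and the primary care provider.

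The study is meant to prepare a multi-site trial. Sites whose claims data cannot be ported to HN-STAR would plausibly need the manual version; this is inferred from the situation at HH and is not stated in the plan. The study would then support the speed of the manual version but say nothing about its correctness.

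**Working it through.** There is no stated figure to reproduce. Section 11.1 says that the study is not powered for formal hypotheses and gives no derivation for the 15 HH patients. The enrolment totals agree: 10 + 30 + 15 = 55.

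**Step 1. The two versions side by side.**

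| | Automated (MSK) | Manual (HH) |
|---|---|---|
| Source (4.2.2) | Billing codes, then NP correction | NP entry from the medical record |
| Data collected (7.3) | NP changes and time | Time |
| Accuracy outcome in 11.2 | Yes, against the electronic record | None |
| Criteria in 11.2 | >90% accurate; median <20 min | Median <30 min |
| Use (4.2.5) | Recommendations and treatment summary | Recommendations and treatment summary |

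**Step 2. What the manual verdict depends on.** Let T be the completion times of the 15 HH checklists and X the number that are accurate. The rule is: feasible if median(T) < 30 minutes. X does not enter it. For any set of times with a median below 30, the verdict is the same for X = 0 and X = 15.

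**Step 3. What the MSK threshold would require if it were borrowed.** 0.90 × 15 = 13.5, so more than 90% means at least 14. 14/15 = 93.3% passes and 13/15 = 86.7% fails.

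**Step 4. How such a rule would behave.** Assume that the 15 checklists are independent and share a true accuracy p. The chance of passing is

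P(X ≥ 14) = 15 p^14 (1 − p) + p^15.

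At p = 0.90 this is 15 × 0.2288 × 0.10 + 0.2059 = 0.549.

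| True accuracy | Chance of passing |
|---|---|
| 70% | 3.5% |
| 80% | 16.7% |
| 90% | 54.9% |
| 95% | 82.9% |
| 98% | 96.5% |

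**Step 5. Precision with 15 patients.** The exact (Clopper-Pearson) 95% intervals are:

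- 13/15: 59.5% to 98.3%
- 14/15: 68.1% to 99.8%
- 15/15: 78.2% to 100% (lower limit 0.025^(1/15) = 0.782)

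The count would expose a poor checklist. It could not establish that true accuracy exceeds 90%, even with 15 of 15 correct.

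**The case against.** The strongest objection is that the two criteria do not test the same thing. Section 11.2 names "the accuracy of the automated treatment summary (verified against the EMR"), and 7.3.1 draws the accuracy data from the NP's changes to what was imported. The natural reading is that the MSK criterion tests the import against the NP-verified record, not the final corrected list. HH has no import to test. A reader might infer that finished MSK checklists pass an accuracy test from which finished HH checklists are excused. The documents do not support that, because the criterion does not independently test the corrected MSK list either. This part of the objection stands.

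A reader might also infer that nothing checks HH entries. That is too strong. Section 13.1 (Quality Assurance) has the research study assistant (RSA) scan HN-STAR data entry monthly for accuracy and completeness, adds prompts for blank or out-of-range fields, and plans annual random-sample audits. Section 13.1.1 stores the checklist itself for both sites, so its content can be audited. But no threshold is attached to any of these, and none is linked to the feasibility decision. The prompts would also miss a plausible but wrong selection.

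The Discussion Guide criterion does not fill the gap. It belongs to another component, concerns missed rather than wrong information, and is rated by the NP, who at HH also completed the checklist.

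Time is a legitimate criterion. Section 3.0 names time and personnel as major barriers to care plans, and 11.2 sets the 30 minutes against an hour or more in practice. Nothing in the documents shows that the criterion would cause haste.

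**Conclusion.** The concern holds in a limited form. The plan can show that the manual checklist is quick, but HH transcription errors cannot alter its feasibility verdict, whatever their number among the 15 checklists. This follows from the text of 11.2 and 7.3.2 and needs no assumption about the error rate.

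The documents give no evidence that HH checklists will be inaccurate; 0 of 15 correct only illustrates what the rule ignores. Nor do they show that an error-prone version would enter the trial unchanged. The verdict covers one component, missing a criterion only prompts consideration of adaptation, and 11.4 foresees adapting content even after a favourable result.

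A hard rule of 14 of 15 would be fragile: a checklist that is truly 90% accurate would fail about 45% of the time (1 − 0.549). The 90% figure is an assumption borrowed from MSK. The gap is worth closing because the check is small and bears on whether the manual version works.

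**What to change.** In 7.3.2, have the HH RSA, not the NP who completed the form, compare each of the 15 submitted checklists with the diagnosis and treatment record, as part of the accuracy scans already planned. Score the checklist as submitted, before any correction.

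In 11.2:

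- Define an accurate checklist on stated fields: site, stage, surgery, radiation and chemotherapy.
- Report the number accurate of 15 with an exact 95% interval.
- State that this result is considered alongside median time when the manual version is judged feasible.
- If the >90% threshold is adopted, state that it means at least 14 of 15, that it is borrowed from the MSK criterion, and that it is imprecise at this sample size.

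The cost is modest RSA time, but more than one extra field on Appendix H. That abstraction covers the year before the visit and the visit itself (7.4.1), whereas treatment ended at least one year before the visit (5.1), so older treatment records must be opened for 15 patients. The other consequence is that the manual version could now fail.

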## **4.1 OVERVIEW OF STUDY DESIGN/INTERVENTION**

### **4.2 Design**

This is a pilot study of HN-STAR for routine follow-up visits in two survivorship clinics – the Head and Neck Survivorship Clinic at MSK and the Survivorship Clinic of the Gray Cancer Center.

Patient Survivorship Program at HH. Each clinic is led by a single NP, [name] at MSK (co-Investigator) and an NP at HH, [name], who is a co-investigator on the HH study team. Each hospital has determined patient eligibility for the clinic. The head and neck survivors seen in each clinic have completed treatment for head and neck cancer at least one year prior and have no evidence of disease. In standard care, the NP provides oncologic follow-up, creates and delivers a survivorship care plan, addresses healthy behaviors, and ensures that the survivor has a primary care provider who will manage general preventive care.

For this pilot study, we will incorporate HN-STAR into a routine NP-led survivorship visit, in order to assess feasibility of HN-STAR in clinical practice. For a single routine visit, each patient will report his or her medical history, preventive care, and symptoms online, and this information (as well as other medical history information) will populate an Interactive Discussion Guide for the NP to use in the clinic visit. In Aim 1: Part 2 of the study, each patient and his or her primary care provider (PCP) will receive the automatically generated Survivorship Care Plan. This study will use surveys at multiple time points during this process to elicit usability and feasibility data from patients, NPs, and PCPs regarding the use of this system (Aim 1).

This study also includes non-survey outcomes assessments. HN-STAR will automatically collect patient reports about symptoms, preventive care, and medical history. Other oncology-related outcomes (such as referrals, medications, and other treatment decisions) will appear in the clinic note for each visit. Both data sources will be used to establish baseline measures and inform feasibility of collecting data for a future trial (Aim 2). In addition, as part of Aim 2, the oncology-related metrics from the clinic visit will enable us to gain preliminary insight into changes after HN-STAR, using a pretest-posttest design.

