### Aim 1: Part 2: Feasibility in clinical practice

There is a designated RSA at MSK and HH who will be responsible for recruitment, enrollment, data collection and study management at their respective site.

*Head and neck cancer survivors.* We will recruit an additional 45 survivors (30 from MSK and 15 from HH) to participate in Aim 1: Part 2 for feasibility testing. Patients who are eligible, scheduled, or due to be seen at the survivorship clinic at MSK and HH will be invited by mail to participate in the HN-STAR study. The patient will be able to opt out of the study by contacting the RSA. If the patient does not opt out, research staff at MSK or HH will follow-up with a phone call. At least three attempts will be made to reach the patient by phone. When the consenting professional at the respective site reaches the patient by phone, she will describe the study and invite interested and eligible patients to participate. The consenting professional will follow a standard consent script as described above. Patients will be consented over the phone with the RSA from their respective study site before completing the

Survivor Self-Assessment before the clinic visit. However, unlike Aim 1: Part 1, participants can complete the Survivor Self-Assessment online at home or in the waiting room before the clinic appointment.

Similar to Aim 1: Part 1, we will enrich for minorities in the MSK clinic by enrolling no more than 20 white non-Hispanic patients at MSK. After enrolling 20 white non-Hispanic patients from MSK, if we have not yet enrolled 30 total patients from MSK, we will only invite non-white or Hispanic patients to participate until 30 patients enroll. With over 20 new survivors seen in this clinic each month, this will not hinder enrollment.

At each study site, each study participant will receive \$50 from the RSA at their study site to provide thanks for their time and effort immediately following completion of the final study survey. This is less than the \$100 incentive for patients in Aim 1: Part 1 because the time and effort will be less for these participants.

*NP.* We will be asking the MSK and HH NP to provide feedback (via survey and interview) about their experience using HN-STAR. Through the consent process, participants will understand that their NP will be surveyed and interviewed about HN-STAR as part of the study. The NPs responsible for head and neck cancer survivors will be asked to provide written consent to participate.

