**Figure 4 continued. Outcome collection**

Assessment	Source	Timing (including end of data collection window)
Survivor Post-Visit Survey	Patient	Following clinic visit, before leaving clinic
Primary Care Provider Survey	PCP	At least one week after being mailed Survivorship Care Plan, within a month of enrollment into study
Passively collected feasibility metrics	HN-STAR	Immediate concurrent data collection via Webcore
Nurse Practitioner Interview	NP	After 30 patients have completed Aim 1: Part 2 at MSK and 15 patients have completed Aim 1: Part 2 at HH, within 1 month of last patient completing Aim 1: Part 2 at the respective site
Survivor Follow-up Interview	Patient	Six months after the clinic visit
Preliminary metrics for future trial (Aim 2)		
Oncologic metrics: Late effects identified and addressed, receipt of head and neck surveillance and appropriate follow-up (e.g. dental exam for those who underwent radiation therapy)	Clinic notes, prescriptions or referrals	Abstracted from any time in the year before the visit (pretest) and in the note pertaining to the clinic visit (posttest)
Non-oncologic metrics: Receipt of routine preventive care (e.g., cancer screening, tobacco cessation)	Survivor Self-Assessment	After completion of the Survivor Self-Assessment

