- >50% of survivors rate the Survivorship Care Plan positively. For survivors, item response will be defined as positive if they report that they strongly agree or agree with the items #25-29 on the Survivor Post-Visit Survey (Appendix E). A survivor will be considered as having a positive overall rating of the Survivorship Care Plan if at least 3 of the five responses are positive.>50% of primary care providers rate the Survivorship Care Plan positively. For primary care providers, item response will be defined as positive if they report that they strongly agree or agree on items #2, 4-6, 8-14. Because of the wording, for items #3 and 7 responses of disagree or strongly disagree will be defined as positive on the Primary Care Provider Survey (Appendix G). If at least 7 of 13 items are positive, we will consider this a positive overall rating to the survivorship care plan.
- If any component does not meet all criteria, we will consider further adapting the component as needed and testing them further in a future protocol.

We will use qualitative data from study interviews to supplement our understanding of usability issues for both the NP and survivors in Aim 1: Part 1. We will use grounded theory to identify salient themes regarding the usability of the Survivor Self-Assessment, the Automated Treatment Checklist, the Interactive Discussion Guide, and the Survivorship Care Plan from the perspectives of both the survivors and the NP.

**11.3 Analysis Aim 2: Collection of preliminary metrics of health care actions.** As described in Section 9.0, relevant metrics for Aim 2 are both oncologic and non-oncologic. We will collect oncologic metrics from any clinic notes that appear in the patient's chart in the year preceding the HN-STAR visit and for the HN-STAR visit itself. Non-oncologic metrics will be collected only from the HN-STAR patient assessment completed before the HN-STAR visit. We will use descriptive statistics to report receipt of oncologic and non-oncologic care.

Also as described in Section 9.0 and listed completely in Appendix H, oncologic outcomes include late effects (symptoms) **identified** and **addressed**, receipt of head and neck surveillance and appropriate follow-up (e.g. dental exam for those who underwent radiation therapy). Non-oncologic outcomes include receipt of recommended routine preventive care (e.g., cancer screening, tobacco cessation).

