Participants may benefit from this study. The NP will receive an Interactive Discussion Guide summarizing medical history, relevant symptoms, and recommendations for care (including symptom management, routine oncologic follow-up, and recommended preventive care). This may help the NP and survivor focus on the most salient issues while promoting the survivor's involvement in his or her care. This may also serve to ensure adherence to current guidelines and promote standardized care for survivors. After the visit, the cancer survivors will receive a Survivorship Care Plan with a plain-language treatment summary and personalized recommendations for ongoing care, which may help the survivors, their primary care providers, and oncology providers plan ongoing management strategies. In Aim 1: Part 2, participants' primary care providers will also receive a Survivorship Care Plan. In addition, survivors will have the opportunity to report their symptoms, engaging the patient in their survivorship care. Further, for the NP who is tasked with providing Survivorship Care Plans as part of routine care in the survivorship clinic, HN-STAR alleviates or minimizes the burden of manual data entry. For primary care providers, they will receive personalized information to help guide the ongoing care of their patients who completed treatment for head and neck cancer.

Another benefit is the knowledge gained from the study. Following curative therapy, head and neck cancer survivors can face significant challenges that impact both quality of life and overall survival. HN-STAR may improve our ability to address oncologic and non-oncologic issues – including surveillance for recurrence, management of late effects of therapy, screening for second cancer, and prevention and treatment of co-morbid illness – during routine survivorship care. This study will evaluate if HN-STAR is feasible in actual practice, if it improves the care provided during the clinical encounter, and if the resulting Survivorship Care Plan is useful to stakeholders. Results from this study will provide critical feedback for modifying HN-STAR and implementing and evaluating it as an intervention in a future multi-center trial.

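### For survivors at their first NP survivorship visit, the Aim 2 before-after difference combines HN-STAR with a change of clinic, and the plan neither limits nor records how many these are

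*Combined protocol and SAP*

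**What the plan says.** Section 11.3 defines the pretest source: "We will collect oncologic metrics from any clinic notes", meaning those in the chart for the year before the HN-STAR visit. Figure 4 in section 9.0 gives the same windows: "Abstracted from any time in the year before the visit (pretest) and in the note pertaining to the clinic visit (posttest"). Neither place restricts pretest notes to the survivorship clinic or to its NP.

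On who may enter Part 2, section 6.0 says "Patients who are eligible, scheduled, or due to be seen at the survivorship clinic at MSK and HH will be invited by mail". The summary in section 1.0 also admits patients due for routine follow-up, and section 5.1 neither requires nor excludes an earlier survivorship visit. On the MSK patient flow, section 6.0 says "With over 20 new survivors seen in this clinic each month, this will not hinder enrollment", while section 11.1 says "The MSK clinic sees over 20 patients per month, ensuring that enrollment is attainable".

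On care without the tool, section 4.2 says "In standard care, the NP provides oncologic follow-up, creates and delivers a survivorship care plan". Section 7.4.1 describes the abstraction as showing change before and after HN-STAR, and the closing paragraph of section 11.3.2 sends the differences in oncologic metrics to the power calculation for the randomized trial. Section 14.1 says the study will evaluate HN-STAR on several points, among them "if it improves the care provided during the clinical encounter".

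**The concern.** A before-after difference can be credited to HN-STAR only if HN-STAR is what changed. For a survivor already followed by the NP, that is roughly the case: same clinic, same clinician, with the tool added. For a survivor at a first NP survivorship visit, every pretest note was written outside that visit type. Clinic, clinician and tool then change together, and the NP visit already brings follow-up and a care plan without the tool.

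Aim 2 exists partly to supply planning inputs. Section 3.0 says the future trial will randomize clinics to HN-STAR or usual care, with changes in late effects identified and managed as primary outcomes. A patient's move into a survivorship clinic is not what that trial randomizes. If the pilot difference contains a transfer component, the trial could be planned on the wrong effect size, and nobody could tell afterwards because the text does not ask for prior-visit status to be kept.

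**Working it through.** The plan gives no effect size, standard deviation, alpha or power, so it has no figure to reproduce. The sample size adds up: 30 + 15 = 45 in Part 2.

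**Can first-visit survivors enter?** Yes. No criterion bars them, and section 6.0 cites over 20 new survivors a month at MSK. Over the six months that section 11.1 expects for enrolling 45 patients, that is more than 20 × 6 = 120 against an MSK target of 30. This shows that new survivors could fill the target, not that they will.

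**Size of the transfer component.** Let f be the share of the 45 who are new to the clinic and D the mean number of late effects identified that the transfer alone would add. The component in the pooled difference is f × D. Both are unknown. The documents mention new survivors only for MSK, so the table takes HH as having none. D is assumed.

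| MSK patients who are new | f | D = 1 | D = 2 | D = 3 |
|---|---|---|---|---|
| 0% | 0/45 = 0 | 0 | 0 | 0 |
| 25% | 7.5/45 = 0.17 | 0.17 | 0.33 | 0.50 |
| 50% | 15/45 = 0.33 | 0.33 | 0.67 | 1.00 |
| 100% | 30/45 = 0.67 | 0.67 | 1.33 | 2.00 |

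A value of f above 0.67 would need new patients at HH as well, on which the documents are silent.

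**What it could do to a power calculation.** All inputs here are assumed: true HN-STAR effect h = 0.5 SD, transfer effect m in SD units, two-sided alpha 0.05, 80% power, individual randomization and no clustering. The apparent effect is d = h + f × m. The planned size is n per arm = 2 × (1.96 + 0.84)² / d², about 15.7/d². Actual power is Φ(h × √(n/2) − 1.96).

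- No new patients: d = 0.50, n = 63, power 80%.
- m = +0.25, half of MSK new: d = 0.58, n = 47, power 68%.
- m = +0.25, all of MSK new: d = 0.67, n = 36, power 56%.
- m = −0.25, half of MSK new: d = 0.42, n = 91, power 92%.
- m = −0.25, all of MSK new: d = 0.33, n = 142, power 99%.

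**A second component.** Section 11.3.1 counts a late effect as identified if a clinic note mentions it. The pretest can draw on a year of notes and the posttest on one, so pooling may raise the pretest count. Writing this window effect as w, the observed difference is HN-STAR effect + f × D + w, with w plausibly negative. At f = 0.67 and D = 2, a w of −1.33 would cancel the transfer component exactly. The sign of f × D + w cannot be settled from the documents.

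**The case against.** The strongest reply is that the documents do not show the MSK sample to be mainly new to the clinic. A reader might infer it by setting over 20 new survivors a month beside over 20 patients a month for the same clinic. These are two rounded lower bounds in different sections, and the first only argues that the cap on white non-Hispanic patients will not slow recruitment. Invitation extends to patients due for a visit, and the study is set in routine follow-up. This stands: f is unknown and may be small.

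Section 7.4.1 can also be read as meaning NP-recorded notes only. That reading does not rescue the analysis. It conflicts with section 11.3, and under it a first-visit survivor has no pretest at all.

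The study is descriptive, not powered for hypotheses, and section 4.2 promises only preliminary insight. That protects the Aim 1 criteria, which are untouched. It does not cover the stated use of the difference in a power calculation.

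Finally, section 3.0 does not define usual care or exclude first-visit patients from the future trial. That also stands. Survivors with a prior NP visit are therefore not automatically the better planning group, and restricting the power calculation to them is not warranted.

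**Conclusion.** The point holds in conditional form. For any first-visit survivor the difference is HN-STAR plus a change of clinic. The pooled difference may therefore mix the two, to an extent the plan neither limits nor records. The transfer component runs from 0 at f = 0 to 0.67 × D if every MSK patient and no HH patient is new (1.33 late effects at the assumed D = 2).

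A reader might go further and conclude that Aim 2 will overstate HN-STAR and leave the next trial underpowered. The documents do not support that. It needs a positive D, a substantial f and a window effect too small to offset them, and none of these is given. What is established is that the difference cannot be interpreted as it stands, with consequences for the future trial's inputs and for the wording of section 14.1.

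**What to change.** 1. During the chart abstraction already planned, record for each pretest note whether it is from the survivorship-clinic NP, and for each survivor whether there was an NP survivorship visit in that year. State how a survivor whose last NP visit was more than a year earlier is classed.
2. In section 11.3, report the oncologic differences separately for prior-visit and first-visit survivors, with the number in each group. Label the first-visit result 'HN-STAR plus clinic transfer'.
3. Do not carry the pooled difference into the power calculation as the HN-STAR effect without showing both estimates and their numbers.
4. Reconcile section 7.4.1 (notes recorded by the NP) with section 11.3 (any clinic notes).
5. Reword section 14.1 so that it does not say the study will evaluate whether HN-STAR improves care.

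The cost is one field per note, one per survivor and a few sentences, with no new patient contact. Appendix H is listed but its content is not in the text reviewed, so the form may already hold part of this. The statistical cost is small groups with imprecise estimates, and possibly too few prior-visit survivors to estimate the HN-STAR-specific difference, in which case the report should say so. Splitting by prior visit does not cure the mismatch between a year of notes and one visit, which needs its own remedy.
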